5.3 Other Outcomes of Interest

- Changes in the ordinal WHO scale from baseline over 14 days
- Length of hospital stay until day 28 in survivors.
- Proportion of participants progressing to mechanical ventilation on day 7 and day 14
- Proportion of participants requiring ICU treatment on day 7 and 14
- Length of ICU stay until day 28
- Ventilator-free days until day 28
- All-cause mortality (time from randomisation to death within four weeks)
- Changes in biomarker levels until day 14: CRP, LDH, D-dimer, ferritin, IL-6, lymphocyte count
- Time to virological clearance of SARS-CoV-2 by PCR from upper or lower respiratory tract samples (time from enrolment to first of 2 negative assays at least 12 hours apart)
- Proportion of patients receiving additional anti-inflammatory treatment such as tocilizumab or immunoglobulins within 14 days
- Time to defervescence (temperature <38.0°C sustained for at least 48 hours)
- Time to clinical improvement (defervescence, normalization of oxygen saturation (>93%) and respiratory rate) until day 28
- Duration of supplemental oxygen until day 28
- Incidence of acute kidney injury classified on the basis of the worst serum creatinine according to the KDIGO classification, and changes of serum creatinine and estimated glomerular filtration rate (eGFR, estimated with the CKD-EPI equation) from baseline
- In a subgroup of patients (in Basel and optional in other centers) the pharmacokinetics and pharmacodynamics of conestat alfa in COVID-19 patients will be characterized by measuring the concentration of conestat alfa and the activity of C1INH, inflammatory cytokines and proteins (such as C4d, C5a, sC5-b9, IL-10) and parameters of the contact activation and coagulation cascade (such as factor XII and pre-kallikrein). In addition, changes of urinary markers of renal injury (such as NGAL, KIM-1, osteopontin and clusterin) from baseline will be analysed.

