6. STUDY DESIGN

6.1 General study design and justification of design

This is an investigator-initiated, exploratory, randomized, parallel-group, open-label, multi-center, phase 2 clinical study in patients with confirmed COVID-19 infection and admitted to the hospital for treatment of SARS-CoV-2 infection to estimate the effect size of conestat alfa treatment in addition to standard of care compared to only standard of care on the proportion of patients surviving without requiring mechanical ventilation.

The study will recruit approximately 120 patients (80 patients in the intervention and 40 in the control arm) from several sites in Switzerland, Brazil and Mexico. Sites will be selected on the basis of estimated numbers of cases, the availability of a committed principal site investigator and research team, and the capacity to collect samples as per protocol.

Participants will be randomly assigned in a 2:1 ratio to conestat alfa treatment in addition to standard of care or only standard of care stratified by the site. Screening, informed consent and randomisation will happen as early as possible after admission to the hospital, usually within 72 hours after admission. Participants will receive intravenous conestat alfa or no additional treatment during a 72-hour period usually starting on the day of informed consent (=day 0). Both groups will continue to receive SOC treatment for COVID-19 infection. Blood samples will be collected before and during the 72-hour administration period. Follow-up will include the period until discharge and a telephone interview at four weeks (+/- one week) if participants are discharged earlier to assess potential adverse events.

Duration of participant's participation will be 4 weeks (+/- 5 days). Screening phase duration is up to 72 hours; treatment phase is a maximum of 72 hours, and follow-up period is 4 weeks after enrolment. At least three attempts will be made to contact the participant or his person of confidence at week 4 before the participant may be considered as lost to follow-up.

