9. STUDY ASSESSMENTS

9.1 Study flow chart(s) / table of study procedures and assessments

Study Periods	Screening	Intervention Period				Follow-up	
		1	2	3	4	5	6
Visit	1	2	3	4	5	6	7
Time (weeks or days, or hours)	d-1 to d0 ¹	d0	d1	d2	d3-13 during admission*	d14 (+/-2d) or discharge	wk4 (+/-5d)
In- /Exclusion Criteria	x						
Patient Information and Informed Consent	x						
Randomisation	x						
Demographics		x					
Medical History and Physical Examination		x				x	
Vital Signs including Respiratory Rate ⁹		x	x	x	x	x	
Laboratory Tests (blood)		x	x		x ³	x	
Virology testing		x ²			x ²	x ²	
Administer Study Medication ⁴		x	x	x	x		
Assessment of WHO ordinal scale		x	x	x	x	x	x
Assessment of ICU admission and/or mechanical ventilation		x	x	x	x	x	x
Laboratory assessment in detail:							
Routine full blood count		x ⁵	x		x ³	x	
Routine coagulation studies		x ⁵	x		x ³	x	
Routine biochemistry including LDH		x ⁵	x		x ³	x	
Serum pregnancy test	x ⁶						
Ferritin, IL-6, D-Dimer		x ⁵	x ¹¹		x ³	x	
C1INH concentration ⁷		x	x			x	
Additional samples in Basel ¹⁰ :		x					
Complement proteins (e.g. C4d, C5a)		x	x		x ³	x	
Inflammatory cytokines (e.g. IL-10)		x	x		x ³	x	
Contact activation and coagulation proteins (e.g. factor XII)		x	x		x ³		
C1INH concentration and activity		x ⁸	x ⁸		x (d3, 7, 10)	x	
Urinary markers of renal injury		x	x		x ³	x	
Blood volume (ml), total/study specific (Basel ¹⁰)	5/5 (5)	12/12 (22)	12/12 (22)		12/5 (10)	12/12 (17)	
Urine volume (ml), study specific in Basel ¹⁰		5	5		5	5	
(Serious) Adverse Events		x	x	x	x	x	x

¹Eligibility criteria have to be assessed within 72 hours after hospital admission. Randomisation may occur on the day of hospital admission.

²Monitoring of SARS-CoV-2 viral load will be performed in Basel and optional in other centers. This will include performance of a quantitative SARS-CoV-2 PCR from upper or lower respiratory tract at baseline

and subsequently once between day 4-7 (according to local standard) and again on day 14 if participants are still admitted or between day 10-13 if discharged earlier. Standard operating procedures include the performance of a second swab following a first negative swab.

³Routine laboratory tests will be performed on days 3, 5, 7, and 10 during hospital admission according to standard procedures of the study site, but will include a set of hematology, coagulation and biochemistry parameters. Additional blood samples will be collected at the same time.

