⁴IMP will be administered during a 64 hour period (+/-4 hours). Trial medication will be stopped in participants that are discharged or transferred to another facility.

⁵Can be omitted if results are available from the same day.

⁶A pregnancy test will be performed in women who may become pregnant, are sexually active, and do not use adequate contraceptive measures.

⁷Collection of samples will be before 1st administration of study medication and subsequently at least 4 hours after the administration of study medication.

⁸Collection of samples will be before 1st administration, 10 (+/-5) minutes after the 1st administration (day 0) and before and 10 (+/-5) minutes after one administration on day 1.

⁹The worst value recorded on a given day will be documented.

¹⁰optional for other centers depending on their ability to collect, centrifuge, aliquot and store blood and urine samples at -80°C.

¹¹IL-6 will not be measured on day 1

* If the patient was already discharged before day 7, the assessment of the WHO ordinal scale will be conducted via a short telephone interview (Score 1 or 2).

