9.2 Assessments of outcomes

9.2.1 Assessment of primary outcome

For the analysis of the primary endpoint, illness severity will be assessed on each day after enrolment (worst status) with the use of the WHO Ordinal Scale for Clinical Improvement (score 0 will be omitted and score 6 and 7 will be combined) and the score on day 7 will be analysed stratified by its baseline value.

Patient State	Descriptor	Score
Uninfected	No clinical or virological evidence of infection	0
Ambulatory	No limitation of activities	1
	Limitation of activities	2
Hospitalized Mild disease	Hospitalized, no oxygen therapy	3
	Oxygen by mask or nasal prongs	4
Hospitalized Severe Disease	Non-invasive ventilation or high-flow oxygen	5
	Intubation and mechanical ventilation	6
	Ventilation + additional organ support – pressors, RRT, ECMO	7
Dead	Death	8

Figure 4: WHO ordinal scale for clinical improvement. For the current study, score 0 will be omitted, and score 6 and 7 will be combined.

The worst score on a given day (between 0:00 and 24:00 hours) will be used for the categorization

Patient State	Description	Score
---------------	-------------	-------

Outpatient	No limitation in activities	1
	Limitation in activities	2
Hospitalized Mild disease	No oxygen therapy	3
	Oxygen by mask or nasal prongs	4
Hospitalized Severe disease	Non-invasive ventilation or high-flow oxygen	5
	Intubation, mechanical ventilation +/- additional organ support	6
Death	Death	7

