9.2.2 Assessment of secondary outcomes

- For the analysis of time to clinical improvement of at least 2 points in the WHO Ordinal Scale for Clinical Improvement, clinical severity will be assessed every day until day 14 according to the Scale with the worst status for that day recorded
- For the analysis of the proportion of patients alive and not having required invasive or non-invasive ventilation at 14 days after enrolment, admission to ICU with invasive or non-invasive ventilation or death will be assessed every day until day 14.
- For the analysis of the proportion of patients with ALI within 14 days after enrolment, PaO₂/FiO₂ will be determined daily until day 14. This is only relevant for patients with arterial blood gas sampling performed in the ICU or rarely on the ward.

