- Only in Basel and in the active treatment group: Collection of blood (5ml) for the analysis of C1INH levels and activity 10 (+/-5 minutes) after the first administration.

Visit 3, Intervention period (Day 1)

- Administration of 4200 U of conestat alfa every 8 hours in the active treatment group as per treatment schedule. The time of dosing and the dose will be recorded.
- Assessment of vital signs including respiratory rate.
- Assessment of WHO ordinal scale and need for oxygen supplementation
- Documentation of ICU admission and/or non-invasive or invasive ventilation
- Collection of blood (12ml) for analysis of ferritin, D-Dimer, C1INH concentration, and in Basel (optional for other centers): collection of blood (5ml) and urine (5ml) for the analysis of complement proteins, parameters of the contact activation and coagulation system, renal injury markers and inflammatory cytokines. Routine full blood count, coagulation and biochemistry studies will only be performed if results from prior tests on the same day are not available.
- Only in Basel and in the active treatment group: Collection of blood (5ml) for analysis of C1INH levels and activity 10 (+/-5 minutes) after any of the three administrations of conestat alfa on that day.

- Assessment of AEs.

Visit 4, Intervention period (Day 2)

- Administration of 4200 U of conestat alfa every 8 hours in the active treatment group as per treatment schedule. The time of dosing and the dose will be recorded.
- Assessment of vital signs including respiratory rate.
- Assessment of WHO ordinal scale and need for oxygen supplementation
- Documentation of ICU admission and/or non-invasive or invasive ventilation
- Assessment of AEs.

Visit 5, Intervention period (Day 3-13 during hospital admission)

- Completion of treatment with conestat alfa (9 administrations in total including the first 8400 U administration) in the active treatment group as per treatment schedule. The time of dosing and the dose will be recorded.
- Assessment of vital signs including respiratory rate.
- Assessment of WHO ordinal scale and need for oxygen supplementation. If the patient was already discharged before day 7, the assessment of the WHO ordinal scale will be conducted via a short telephone interview (Score 1 or 2).
- Documentation of ICU admission and/or non-invasive or invasive ventilation

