- Routine laboratory tests will be performed on days 3, 5, 7 and 10 during admission according to standard procedures, and should include a set of hematology, coagulation and biochemistry parameters. Additionally, blood (5ml) for analysis of ferritin, IL-6, D-Dimer, C1INH concentration will be collected at the same time point, and in Basel (optional for other centers): collection of blood (5ml) and urine (5ml) for the analysis of complement proteins, parameters of the contact activation and coagulation system, renal injury markers and inflammatory cytokines.
- Virological assessment (quantitative SARS-CoV-2 PCR in respiratory specimen) should be performed on day 4-7 (according to local standard). This is optional for all centers except Basel.
- Assessment of AEs

Visit 6, Follow-up (Day 14 (+/-2 days) or at discharge)

- Physical examination including body weight.
- Assessment of vital signs including respiratory rate.
- Assessment of WHO ordinal scale and need for oxygen supplementation
- Documentation of ICU admission and/or non-invasive or invasive ventilation
- Laboratory assessment including routine hematology, coagulation and biochemistry studies (7ml). Routine laboratory tests will be performed every second day during admission according to standard procedures. Additional sample collection will be required in patients without routine testing on the day of discharge. Additionally, blood (5ml) for analysis of ferritin, IL-6, D-Dimer, C1INH concentration will be collected at the same time point, and in Basel (optional for other centers): collection of blood (5ml) and urine (5ml) for the analysis of complement proteins, renal injury markers and inflammatory cytokines.
- Virological assessment (quantitative SARS-CoV-2 PCR in respiratory specimen) will be performed on day 14 (when still admitted) or at discharge if on day 10-13. This is optional for all centers except Basel.
- Assessment of AEs.

Visit 7, Follow-up (week 4 +/- 5 days, telephone interview or study visit if still admitted)

- Assessment of adverse events, WHO ordinal scale, admission to ICU and/or mechanical ventilation by structured telephone interview. If necessary, medical charts will be reviewed, discharge summaries will be obtained or the patients' general practitioner will be contacted regarding specific follow-up information.

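### Daily WHO scoring to day 14 is required by Sections 9.2.1 and 9.2.2 but not delivered by the visit schedule, so the exploratory 14-day change is missing or too high for patients who go home (minor)

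*Protocol*

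**What the plan says.** Two parts of the protocol describe how often the WHO scale is scored.

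**Outcome text.** Section 9.2.1 says "illness severity will be assessed on each day after enrolment (worst status"; Section 9.2.2 says "clinical severity will be assessed every day until day 14 according to the Scale with the worst status for that day recorded". Neither is restricted to inpatients. The outcome these scores would feed is "Changes in the ordinal WHO scale from baseline over 14 days" (Section 5.3).

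**Operational text.** The flow chart in Section 9.1 heads the relevant column "d3-13 during admission", and Section 9.3.1 repeats the restriction for Visit 5. The next visit is "Visit 6, Follow-up (Day 14 (+/-2 days) or at discharge". The footnote to the days 3 to 13 column adds one contact: "If the patient was already discharged before day 7, the assessment of the WHO ordinal scale will be conducted via a short telephone interview", with score 1 or 2. Section 6.1 describes the general plan in the same way: "Follow-up will include the period until discharge and a telephone interview at four weeks (+/- one week) if participants are discharged earlier". The week-4 contact includes a WHO score.

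The score used for a day is the worst between 0:00 and 24:00 (Section 9.2.1). LOCF is stated only for the primary variable (Sections 11.4.1 and 11.5). Other outcomes of interest are to be analysed descriptively and exploratively (Section 11.4.3).

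**The concern.** A site that follows the flow chart stops scoring at discharge. A site that follows Section 9.2.2 would contact discharged patients daily to day 14. Both read the same protocol, so what is collected could differ by site.

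Under the flow chart, whether an outpatient score exists in the window depends on when the patient recovered, which is the outcome itself. Scores 1 and 2 can enter the 14-day course only through the call for patients discharged before day 7. For everyone else who goes home, the last recorded value is an inpatient score. A summary that uses only recorded values, or that treats Visit 6 as day 14, would understate benefit in the arm that discharges more patients.

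**Working it through.** **Step 1: follow individual records through the schedule.**

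- Baseline 4, discharged on day 9. Scores exist for days 0 to 9. Visit 6 falls on day 9, and because the worst status of that day counts, it is an inpatient score, say 3 or 4. The patient left after day 7, so there is no call. Days 10 to 14 are empty until week 4. True day-14 score at home: 1 or 2, a change of -3 or -2. Recorded: nothing at day 14, or a Visit 6 change of -1 or 0.
- Baseline 4, discharged on day 5. Visit 6 falls on day 5 with an inpatient score, the call gives 1 or 2, and day 14 is empty.
- Still admitted on day 14, with Visit 6 on that day: complete.

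**Step 2: size of the effect on a day-14 summary.** The protocol gives no figure to reproduce and no day-14 distribution, so the following distributions are assumptions. Baseline is 4 for all, so the difference in mean change equals the difference in mean score.

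| Scenario, arm | 1 | 2 | 3 | 4 | 5 | 6 | 7 |
|---|---|---|---|---|---|---|---|
| A conestat | .40 | .35 | .03 | .07 | .03 | .06 | .06 |
| A control | .30 | .30 | .06 | .16 | .04 | .07 | .07 |
| B conestat | .45 | .35 | .02 | .06 | .02 | .05 | .05 |
| B control | .30 | .30 | .05 | .15 | .05 | .075 | .075 |
| C conestat | .40 | .35 | .04 | .09 | .03 | .045 | .045 |
| C control | .30 | .30 | .064 | .144 | .048 | .072 | .072 |

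Let D be the share at home (scores 1 and 2) and H the sum of score times share over scores 3 to 7.

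- A: D = .75 vs .60, H = 1.30 vs 1.93
- B: D = .80 vs .60, H = 1.05 vs 1.975
- C: D = .75 vs .60, H = 1.215 vs 1.944

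Mean scores by approach:

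- everyone at the true score: p1 + 2·p2 + H
- only patients in hospital or dead: H / (1 - D)
- every discharged patient at a common value v: v·D + H, where v = 3 or 4 imitates using the Visit 6 inpatient score and v = 1 or 2 is a common outpatient rule

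Difference, conestat minus control (negative favours conestat):

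| Approach | A | B | C |
|---|---|---|---|
| True scores, all patients | 2.40 - 2.83 = -0.43 | 2.20 - 2.875 = -0.675 | 2.315 - 2.844 = -0.529 |
| In hospital or dead only | 5.20 - 4.825 = +0.375 | 5.25 - 4.9375 = +0.3125 | 4.86 - 4.86 = 0.00 |
| Visit 6 score, v = 3 | 3.55 - 3.73 = -0.18 | 3.45 - 3.775 = -0.325 | 3.465 - 3.744 = -0.279 |
| Visit 6 score, v = 4 | 4.30 - 4.33 = -0.03 | 4.25 - 4.375 = -0.125 | 4.215 - 4.344 = -0.129 |
| Common rule, v = 1 | 2.05 - 2.53 = -0.48 | 1.85 - 2.575 = -0.725 | 1.965 - 2.544 = -0.579 |
| Common rule, v = 2 | 2.80 - 3.13 = -0.33 | 2.65 - 3.175 = -0.525 | 2.715 - 3.144 = -0.429 |

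With 80 and 40 patients, the in-hospital-or-dead comparison rests on 20 vs 16 patients in A and C (80 × .25; 40 × .40) and 16 vs 16 in B (80 × .20).

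**Step 3: what drives the shift.** With a common v, each point by which discharged patients are scored too high moves the difference towards control by the gap in discharge rates, here .15 or .20. This does not depend on the mix of remaining inpatients. The in-hospital-or-dead result does: it is reversed in A and B, where the patients left on conestat are assumed sicker, and zero in C, where the mix is the same in both arms.

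**The case against.** A reader might infer that the 14-day change cannot be derived at all for discharged patients. The documents do not support that. By the scale's definition a living outpatient scores 1 or 2, and the protocol uses this itself in the footnote on the call. Discharge dates and four-week mortality are recorded (Section 9.2.3). Week 4 adds a WHO score with chart review or contact with the general practitioner where needed (Section 9.3.1), and participants are asked to report new hospital admissions (Section 9.2.4.1). For a survivor who is not readmitted, only the distinction between 1 and 2 is lost.

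A reader might also infer that a real benefit will vanish or reverse in the reported result. That requires an analysis that drops discharged patients. No section prescribes one: the FAS is everyone randomised, and the handling of other outcomes is deferred to a statistical analysis plan that is not shown here. The distributions above are assumed, so they show the direction and possible size of the distortion, not an expected result.

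Both replies stand and limit the point. They do not remove the conflict over what sites must collect. A later analysis plan can assign a value to discharged patients, but it cannot recover a distinction between 1 and 2 that nobody recorded. The footnote does not name the day of the call. A single call to obtain the day-7 score is the natural reading, and on any reading it omits patients discharged on day 7 or later.

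**Conclusion.** The point holds as an internal contradiction of minor severity. Sections 9.2.1 and 9.2.2 require daily scores to day 14; Sections 9.1 and 9.3.1 do not collect them after discharge, apart from the call for discharge before day 7. Followed as scheduled, the 14-day change is missing, or taken from an inpatient score, because the patient recovered. On the assumed distributions a true difference of -0.43 to -0.675 shrinks to between -0.03 and -0.325 if Visit 6 stands for day 14, and becomes 0.00 to +0.375 if only patients in hospital or dead are summarised. Any common outpatient score of 1 or 2 keeps the direction, at -0.33 to -0.725.

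The consequence is confined to one exploratory, descriptive outcome. The day-7 primary endpoint has its own call for patients discharged earlier, and time to clinical improvement counts live discharge as an event, so neither depends on the missing scores.

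**What to change.** Reconcile Sections 9.1 and 9.3.1 with 9.2.1 and 9.2.2 in one of two ways:

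- Extend the short telephone score to day 14 for every patient discharged earlier, and say so in the schedule. Cost: one short call per discharged patient and one line in the flow chart. If only a day-14 score is wanted after discharge, reword the daily requirement to match.
- Or state that scoring stops at discharge, and give every living, non-readmitted discharged patient a score by one common rule, the same in both arms and irrespective of discharge date, for example a merged outpatient category 1 to 2. Cost: one derivation rule and the loss of the distinction between 1 and 2.

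In both cases take death and readmission from the week-4 data and analyse all randomised patients. Do not combine telephone scores for early discharges with a fixed score of 2 for later ones: the value would then depend on when the patient left, which tends to favour the arm that discharges faster. Do not extend LOCF to this outcome, since it can carry an inpatient score into days at home.
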